4. SUMMARY OF STUDY DESIGN

In this Phase 3 clinical study, approximately 750 subjects with mild-to-moderate AD will receive placebo or 100 mg tablets of simufilam, twice daily, for 52 weeks. Randomization (1:1) will be stratified by low or high MMSE (16-20 and 21-27).

Subjects, 50-87 years of age, will be selected for screening based on a diagnosis of AD consistent with Stages 4 or 5 on the Alzheimer's continuum (National Institute on Aging – Alzheimer's Association 2018⁵). Subjects must have MMSE \geq 16 and \leq 27, and a Clinical Dementia Rating Global Score (CDR-GS) of 0.5, 1 or 2. Finally, subjects must have confirmed PET or fluid biomarker evidence of AD pathophysiology prior to randomization (see Section 5.2 – Inclusion Criteria for details).

Once subjects have been satisfactorily screened for study participation, visits to the research clinic will occur on Study Day 1 and at Weeks 4, 16, 28, 40 and 52.

The co-primary endpoints include the 12-item Alzheimer's Disease Assessment Scale – Cognitive Subscale (ADAS-Cog12) and the Alzheimer's Disease Cooperative Study – Activities of Daily Living (ADCS-ADL), both assessed as the change from baseline to the end of the double-blind treatment period (Week 52).

Secondary endpoints include the integrated Alzheimer's Disease Rating Scale (iADRS), Neuropsychiatric Inventory (NPI), MMSE, and Clinical Dementia Rating Sum of Boxes (CDR-SB). A brief questionnaire assessing caregiver burden, the Zarit Burden Interview (ZBI), will be collected as an additional secondary endpoint.

Safety will be evaluated by adverse event monitoring, vital signs, clinical labs, and the Columbia Suicide Severity Rating Scale (C-SSRS) at every visit. Subjects will undergo MRI during screening to ensure entry criteria are met (unless recent MRI confirms entry criteria). Resting ECGs will be conducted at Baseline (Study Day 1) and Weeks 4, 28 and 52. A complete physical and neurological examination will be performed at screening, and brief examinations will be performed at all other visits. Weight will be measured during the Screening Period, at Baseline (Study Day 1) and at all other visits.

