- 9. Male subjects must be willing to use contraception during the study. With female partners of childbearing potential, male subjects, regardless of their fertility status, must agree to either remain abstinent or use condoms in combination with one additional highly effective method of contraception (e.g., oral or implanted contraceptives, or intrauterine devices) or an effective method of contraception (e.g., diaphragms with spermicide or cervical sponges) during the study and for 14 days after study drug dosing has been completed.
- 10. Fluency in a language of the research site and the utilized assessment materials.

- 11. Has adequate visual and auditory acuity (in the Investigator's judgment) that is sufficient to complete all scheduled assessments (eyeglasses and hearing aids are permitted).
- 12. If receiving background AD medications, including cholinesterase inhibitors, memantine, neuroleptics, anxiolytics, or sleep medications, the dosing regimen must be stable for at least 12 weeks prior to Study Day 1 (randomization) and should be expected to remain stable during the study (Note barbiturates, meprobamate, and high dose benzodiazepines are not allowed, while low dose benzodiazepines, zolpidem, zaleplon and suvorexant are permitted). Chronic medications for conditions other than AD (such as depression) must be prescribed at a stable dose for at least 4 weeks prior to screening. Medications that might have a potential confounding effect on cognitive testing (either prescription or non-prescription medications) should not be modified during the Screening Period (see Section 6.3 for additional details).
- 13. The subject has not been a cigarette smoker or chewed tobacco for at least 3 years (occasional pipe or cigar smoking is permitted, but vaping is not).
- 14. Availability of a person (a study partner) who has frequent and sufficient contact with the study subject (defined as ≥ 10 hours per week), and can:
 - a. provide accurate information regarding the study subject's cognitive and functional abilities in the opinion of the Investigator,
 - b. agree to comply with and participate at all scheduled visits and study procedures,
 - c. sign the necessary consent form,
 - d. maintain the same level of interaction with the study subject throughout the study duration.

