7.1. EVALUATIONS BY VISIT

Follow-up visits can be scheduled +/- five (5) days from the targeted Study Visit date.

7.1.1. Screening Period (No greater than a 60-day duration prior to Study Day 1)

The Sponsor recognizes the Screening Period assessments and procedures may not necessarily be completed in a single visit. A subject is permitted to be screened over more than one calendar day if, in the Investigator's judgment, such scheduling will optimize the accuracy of Screening Period assessments and procedures. The following will be completed during the Screening Period:

- Informed Consent.
- Review of Inclusion and Exclusion Criteria
- Collect demographic information (e.g., sex, date of birth, race/ethnicity, level of education)
- Medical and surgical history
- Review concomitant medications and any recently discontinued medications.
- To the extent such information is available, review and record any investigational drugs administered during past clinical study participation regardless of the date of such participation.

- History of drug, alcohol and tobacco use
- eCOA order of administration at screening:
 - o Note it is a study requirement to first administer the MMSE (and then the other assessments if the MMSE criterion is met)
 - MMSE
 - CDR (study partner is interviewed first in the absence of the study subject and then the subject is interviewed, by the same rater, in the absence of the study partner)
 - Geriatric Depression Scale
 - C-SSRS Baseline/screening version
- Complete physical and neurologic examination; including measurement of key vital signs (blood pressure [supine], temperature, pulse rate), height and weight (to calculate BMI)
- A 12-lead resting ECG (5-min supine)
- Laboratory assessments, including routine serum chemistry, TSH, free T4, Vitamin B12 levels, HBsAg, HCV-Ab, hematology, urinalysis and urine screen for drugs of abuse. Plasma for P-tau181 or P-tau217 assessment will also be collected unless there is documented evidence of AD pathophysiology prior to screening. For subjects with diabetes, collect a blood sample for HbA1C. Unexpected, abnormal laboratory results observed during the Screening Period should be captured as Medical History and not as an AE (see Section 10.1 Adverse Events Definition).

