7.1.7. End-of-study / Early Termination Safety Follow-up

The subject and/or study partner will receive a follow-up phone call 7-14 days after the last dose of Study Drug for adverse event monitoring. If needed, a follow-up clinic visit will be scheduled. This phone call will thus occur Week 53 to 54 for those subjects who complete all study visits, or 1 to 2 weeks after Early Termination. If the subject reports an adverse event, the subject should be followed and treated by the Investigator until the AE has resolved or stabilized (see Section 10.1 – Adverse Events).

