7.1.10 Stopping Criteria

Liver chemistry threshold stopping criteria have been designed to ensure subject safety and to evaluate liver event etiology during administration of Study Drug. Potential discontinuation of Study Drug for abnormal liver function tests should be considered by the Investigator in consultation with the designated medical monitor if the study subject meets one or more of the following criteria:

- ALT or AST \geq 4x ULN;
- ALT or AST \geq 3x ULN and total bilirubin \geq 2x ULN;
- ALT or AST ≥ 3x ULN if associated with the appearance or worsening of fatigue, nausea, vomiting, right upper quadrant pain or tenderness, fever, rash and/or eosinophilia; or
- ALP elevations, if deemed of liver origin and drug-related as follows:
 - o ALP > 3x ULN;
 - o ALP > 2.5x ULN and total bilirubin > 2x ULN; or
 - o ALP > 2.5x ULN if associated with the appearance or worsening of fatigue, nausea, vomiting, right upper quadrant pain or tenderness, fever, rash and/or eosinophilia.

In the event of discontinuation due to abnormal liver function tests, the subject will be appropriately investigated to determine the potential cause and referred to a physician experienced in the treatment of hepatic disorders.

Study drug should be discontinued if a subject: (1) positively affirms suicidal ideation in response to questions number 4 or 5 in the suicidal ideation section of the C-SSRS, or (2)

Page 36 of 52

CONFIDENTIAL

reports any suicidal behavior or non-suicidal self-injurious behavior since their last visit in response to the C-SSRS Suicidal Behavior questions. The subject should be referred to a psychiatrist or an appropriate health care professional for further evaluation and management.

Bodyweight loss (compared to weight at Baseline Visit [Study Day 1]) of ≥ 2 kg resulting in a BMI < 18.5 is an additional stopping criterion.

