10. ADVERSE EVENTS/SERIOUS ADVERSE EVENTS

10.1. ADVERSE EVENTS - DEFINITION

An Adverse Event (AE) is any undesirable event that occurs to a subject during a study, whether or not that event is considered related to Study Drug. Monitoring for AEs will start after informed consent has been obtained. Examples include:

- Any treatment-emergent signs and symptoms (events that are marked by a change from the subject's baseline/entry status [e.g., an increase in severity or frequency of pre-existing abnormality or disorder])
- All reactions from Study Drug, an overdose, abuse of drug, withdrawal phenomena, sensitivity or toxicity to Study Drug
- Apparently unrelated illnesses
- Injury or accidents (Note: if a medical condition is known to have caused the injury or accident, the medical condition and the accident should be reported as two separate medical events [e.g., for a fall secondary to dizziness, both "dizziness" and "fall" should be recorded separately])
- Extensions or exacerbations of symptoms, subjective subject-reported events, new clinically significant abnormalities in clinical laboratory, physiological testing or physical examination

All AEs, whether or not related to Study Drug, must be fully documented on the AE page of the CRF and in the subject's clinical chart. Adverse events reported during the screening period or AEs secondary to study-related procedures should always be captured as not having a reasonable possibility the AE was caused by the Study Drug. Unexpected, abnormal laboratory results observed during the Screening Period should be captured as Medical History and not as an AE.

In the event that a subject is withdrawn from the study because of an AE, it must be recorded on the CRF as such. The subject should be followed and treated by the Investigator until the abnormal parameter or symptom has resolved or stabilized.

The Investigator must report all directly observed AEs and all spontaneously reported AEs. The Investigator will ask the subject a non-specific question (e.g., "Have you noticed anything different since your dose of the study medication?") to assess whether any AEs have been experienced since the last assessment. AEs will be identified and documented in the Electronic Data Capture (EDC) system in appropriate medical terminology. The severity and the relationship to the Study Drug will be determined and reported in EDC (see below).

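### Protocol Section 10.1 puts the only solicited adverse-event question to the subject, who has dementia and about 12 weeks to recall, and does not require the attending study partner to be asked

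*Protocol*

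**What the plan says.** Protocol Version 3.0, Section 10.1, describes how AEs are found at visits: "The Investigator will ask the subject a non-specific question", with the purpose "to assess whether any AEs have been experienced since the last assessment". The sentence before it adds a second source: "The Investigator must report all directly observed AEs and all spontaneously reported AEs". It does not restrict who may make a spontaneous report.

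Sections 7.1.3 to 7.1.6 list AE monitoring at each visit without naming an informant. Sections 10.2 and 10.3 base severity and relationship on factors that include the subject's report; neither mentions the partner.

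On timing, Section 4 says that "visits to the research clinic will occur on Study Day 1 and at Weeks 4, 16, 28, 40 and 52", and Section 7.1 that "Follow-up visits can be scheduled +/- five (5) days from the targeted Study Visit date".

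On the partner, inclusion criterion 14 in Section 5.2 requires someone who will "agree to comply with and participate at all scheduled visits and study procedures". Section 7.1.3 has the partner instructed to give the study drug. The partner becomes a named AE contact only in Section 7.1.7: "The subject and/or study partner will receive a follow-up phone call". Under Section 7.1.8 that call is not made for subjects who enter the open-label extension.

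Section 7.1.10 lists six liver-chemistry criteria. Two apply "if associated with the appearance or worsening of fatigue, nausea, vomiting, right upper quadrant pain or tenderness", or with certain other listed findings.

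**The concern.** Self-report after about 12 weeks is a weak instrument in this population. Section 5.2 admits subjects who cannot give written consent and foresees that some will lose capacity during the study. For function, behaviour and global rating the protocol does not rely on the subject alone: the partner informs the ADCS-ADL, the NPI and the CDR, and the depression scale takes caregiver input. The solicited AE question is the exception.

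Safety is part of the primary objective (Protocol Section 3), and AE incidence is the first safety endpoint listed in SAP Section 3.2.2. A symptom that came and went between visits, was seen by no one at the site and was forgotten by the subject could go unrecorded even though the person best placed to report it is at the clinic. Two liver criteria also need symptom information.

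**Working it through.** **1. Recall period.** Target days are Day 1 (baseline) and Days 29, 113, 197, 281 and 365 (SAP Table 2.1).

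- Differences: 29 − 1 = 28; 113 − 29 = 84; 197 − 113 = 84; 281 − 197 = 84; 365 − 281 = 84 days.
- Four of five intervals are therefore 84 days (12 weeks). They cover 4 × 84 = 336 of 28 + 336 = 364 days, or 92% of the scheduled treatment period.
- With the 5-day window used at both ends, an interval can reach 84 + 10 = 94 days (13.4 weeks).

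**2. Who is asked, set against who is present.**

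| Contact | Person named for AE questioning | Partner's role |
|---|---|---|
| Day 1 to Week 52 visits | Subject (Section 10.1) | Required at all visits; informs ADCS-ADL and ZBI each time, NPI at Day 1, Week 28 and Week 52, CDR at Week 52 |
| Call 7-14 days after last dose | Subject and/or partner (Section 7.1.7) | Named AE contact; call omitted for extension entrants |

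A subject who enters the extension therefore has no contact in this study at which the partner is named as an AE informant. Sections 7.1.3 to 7.1.6 also allow subject and partner scales to be run in parallel in separate rooms, so attendance alone does not mean that the partner hears the AE question.

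**3. What other routes detect.** Every follow-up visit has vital signs, weight, brief physical and neurologic examination, medication review, laboratory tests and the C-SSRS; ECGs are done at Weeks 4, 28 and 52. Except for the medication review and the C-SSRS, these show the state on the day of the visit. Nausea, vomiting or dizziness that resolved weeks before may leave no trace in them.

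**4. Reach into the liver criteria (Section 7.1.10).**

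| Criterion | Symptom element |
|---|---|
| ALT/AST ≥4x ULN | No |
| ALT/AST ≥3x ULN and bilirubin ≥2x ULN | No |
| ALT/AST ≥3x ULN with listed symptoms or signs | Yes |
| ALP >3x ULN | No |
| ALP >2.5x ULN and bilirubin >2x ULN | No |
| ALP >2.5x ULN with listed symptoms or signs | Yes |

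The symptom branch alone decides only for ALT/AST from 3x to below 4x ULN with bilirubin below 2x, and for ALP above 2.5x up to 3x ULN with bilirubin no higher than 2x. Within those bands, fever, eosinophilia and abdominal tenderness can be picked up by temperature, white-cell differential and examination. Fatigue, nausea, vomiting and pain depend on report.

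**5. Illustration of size.** The documents give no AE rate and no capture rate, so every input here is an assumption. Let s be the fraction of events captured by all routes together, equal in both arms. Observed rate = s × true rate, so observed difference = s × true difference, and the relative risk does not change.

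| s | Observed rates (true 10% and 5%) | Difference | Relative risk |
|---|---|---|---|
| 1.0 | 10.0% and 5.0% | 5.0 points | 2.0 |
| 0.9 | 9.0% and 4.5% | 4.5 points | 2.0 |
| 0.5 | 5.0% and 2.5% | 2.5 points | 2.0 |

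**The case against.** The best defence is that Section 10.1 does not make the subject's answer the only source. Directly observed and spontaneous AEs must be reported, from whomever they come, and new clinically significant laboratory, physiological or examination findings are themselves AEs. Unscheduled visits for AEs are provided for (Section 7.1.9), and a subject with an SAE is told to contact the study physician (Section 10.5). Nothing keeps the partner out of the conversation; where the protocol wants the two apart, as for the CDR, it says so. Many sites will ask the partner anyway. SAP Section 9 summarises safety descriptively, with no inferential tests unless otherwise specified, so the loss does not weaken a specified test of AE rates.

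All of that is correct and limits the point. It does not remove it: a partner's report is allowed, but nothing requires that it be sought, and practice may vary between sites.

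A reader might go further and infer that AEs will be under-reported. The documents hold no ascertainment data, so only a risk can be claimed. A reader might also expect reporting to drift with cognition, so that an effective drug raises AE reports in the active arm. That is conceivable, but nothing in the documents shows it.

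**Conclusion.** The point holds as a correctable weakness in the elicitation rule. Section 10.1 names only the subject for the one solicited question, over about 12 weeks at four of five post-baseline visits, and leaves asking the attending partner to discretion. The events at risk are transient, symptomatic and unobserved ones.

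The size is unknown. The direction, lower AE rates and smaller absolute differences, rests on the assumption that the loss is similar in both arms; relative risks would then be unaffected. The 0.5 to 0.9 range is illustrative only.

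A reader might infer that the liver criteria as a whole are compromised. They are not: four of the six need no symptom information, and the other two are affected only within the bands shown and only for fatigue, nausea, vomiting and pain.

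**What to change.** Amend Section 10.1 so that at every visit the Investigator puts the non-specific question, about any change since the last assessment, to both the subject and the study partner. This goes further than Section 7.1.7, which accepts either person, but extends a role for the partner that the protocol already recognises there.

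The cost is one sentence and roughly a minute per visit (an estimate), with no extra visit because the partner already attends. Somewhat more minor AEs will be recorded. SAP Section 2.2 reports the final sample of 804 as already randomised, so a change made at that stage reaches only the remaining visits and alters ascertainment part-way through. It would apply equally to both arms. The study report should give the date of the change and state the limitation for visits completed before it.

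Recording on the AE page who reported the event would be useful but is optional, since it needs a CRF change. No change to any clinical threshold or stopping criterion is proposed.

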10.2. ADVERSE EVENTS - SEVERITY RATING

The severity of each AE should be characterized and then classified into one of three clearly defined categories as follows:

- Mild the AE does not interfere in a significant manner with the subject's normal functioning level. It may be an annoyance.
- Moderate the AE produces some impairment of functioning but is not hazardous to health. It is uncomfortable or an embarrassment.
- Severe the AE produces significant impairment of functioning or incapacitation and is a definite hazard to the subject's health.

These three categories are based on the Investigator's clinical judgment, which in turn depends on consideration of various factors such as the subject's report and the physician's observations. The severity of the AE should be recorded in the appropriate section of the EDC.

10.3. ADVERSE EVENTS – RELATIONSHIP TO STUDY DRUG

The relationship of each AE to the Study Drug will be based on the Investigator's assessment as to whether there is a reasonable possibility the AE was caused by the Study Drug. This assessment will be based on the Investigator's clinical judgment, which in turn depends on consideration of various factors such as the subject's report, the timing of the AE in relationship to Study Drug administration/discontinuation, the Investigator's observations, and the Investigator's prior experience. The Investigator's assessment of the relationship of the AE to the Study Drug will be recorded in the appropriate section of the EDC.

10.4. SERIOUS ADVERSE EVENTS AND UNEXPECTED ADVERSE EVENTS - DEFINITIONS

A Serious Adverse Event (SAE) includes (but is not limited to) an experience occurring at any dose that results in any of the following outcomes:

- Death
- A life-threatening event (i.e., the subject is at immediate risk of death from the reaction as it occurs). "Life-threatening" does not include an event that, had it occurred in a more serious form, might have caused death. For example, druginduced hepatitis that resolved without evidence of hepatic failure would not be considered life-threatening even though drug-induced hepatitis can be fatal.
- In-patient hospitalization (hospital admission, not an emergency room visit) or prolongation of existing hospitalization.

- A persistent or significant disability/incapacity (i.e., a substantial disruption of the subject's ability to carry out normal life functions).
- A congenital anomaly/birth defect.

In addition, medical and scientific judgment should be exercised in deciding whether other situations should be considered an SAE (i.e., important medical events that may not be immediately life-threatening or result in death but may jeopardize the subject or may require medical or surgical intervention to prevent one of the other outcomes listed in the definition above). Examples of such medical events include (but are not limited to): allergic bronchospasm requiring intensive treatment in an emergency room or at home, blood dyscrasias or convulsions that do not result in in-patient hospitalization, or the development of drug dependency or drug abuse.

An **unexpected** AE is one for which the specificity or severity is not consistent with the current Investigator's Brochure. For example, hepatic necrosis would be unexpected (by virtue of greater severity) if the Investigator's Brochure listed only elevated hepatic enzymes or hepatitis.

Similarly, cerebral thromboembolism and cerebral vasculitis would be unexpected (by virtue of greater specificity) if the Investigator's Brochure listed only cerebral vascular accidents.

